16.1 DATA MANAGEMENT ISSUES

A Research Study Assistant (RSA) will be assigned to the study. The responsibilities of the RSA include project compliance, data collection, abstraction and entry, data reporting, regulatory monitoring, problem resolution and prioritization, and coordination of the activities of the protocol study team.

The data collected for this study will be entered into the Clinical Research Database (CRDB). Source documentation will be available to support the computerized patient record.

16.1.1 Data Management Requirements for Participating Sites

Data

Standardized Case Report Forms (CRFs) and directions for use and sign off requirements have been generated for this study. Blank case report forms will be sent to the study staff at each participating site for use. The participating Site PI is responsible for ensuring these forms are completed accurately, legibly and in a timely manner.

Source Documentation

Source documentation refers to original records of observations, clinical findings and evaluations that are subsequently recorded as data. Source documentation should be consistent with data entered into CRFs. Relevant source documentation to be submitted throughout the study includes:

For Step 1:

• Pathology report confirming ER/PR/AR status.

For Step 2:

- o Baseline measures to assess pre-protocol disease status
 - o Medical history
 - o Physical examination, including height and weight measurement
 - ECOG performance status
 - Vital signs
 - Prior medication evaluation
 - Laboratory tests (CBC, comprehensive panel, tumor markers)
 - Bone scan or PET Scan
 - CT Chest/Abdomen/Pelvis
 - Pathologic confirmation of breast cancer and hormone receptor status
- o Laboratory records
- o Treatment records
- o Toxicities/adverse events not previously submitted with SAE Reports
- Response designation

16.1.2 Data and Source Documentation Submission for Participating Sites

Participating sites should fax CRFs and source documentation to MSKCC to the contact provided below. Submissions should include a cover page listing all CRFs enclosed per participant.

[contact] to the attention of Protocol 07-022 Research Staff

16.1.3 Data and Source Documentation Submission Timelines for Participating Sites

Data and source documentation to support data should be transmitted to MSKCC according to chart 16.0.3.1:

Data and Source Submission Requirements and Timelines for Therapeutic Studies

IRB#: 07-022A(13)

	Baseline	Visit 1	Visit 2	Visit 3	Visit 4	SAE	Off Study			
SUBMISSION SCHEDULE										
Source Documentation	Within 24 hours (see section 15.1.1)	with	in 14 days	of the end o	f cycle	Within 3 days of event (see section 17.2.1); updates to	Within 14 days of			
CRFs	Within 7 days of visit					be submitted as available	visit			
Required Forms										
Demographics/Disease Form ¹	Х									
Patient Disease	Х									
Concomitant Medications Form	Х	Х	Х	Х	Х		Х			
Diagnostic Test Form	Х									
Physical Exam Form	Х	Х	Х	Х	Х		Х			
Pathology Form	Х									
Treatment Form		Х	Х	Х	Х		Х			
Laboratory Form	Х	Х	Х	Х	Х		Х			
Treatment Modification Form		Х	Х	Х	Х					
Past Treatment Form	Х									
Comorbidity	Х									
Lesion/EOD Form					V ¹		Х			
Toxicity Form	Х	Х	Х	Х	Х	Х	Х			
Serious Adverse Event Form						Х				
Hospitalization Form						Х				
Protocol Outcome				Х			Х			
Patient Status Form	atianta this is the only for						Х			

¹ For step 1 ineligible patients, this is the only form required.

16.1.4 Data Review and Queries for Participating Site Data

Research staff at MSKCC will review data and source documentation as it is submitted. Data will be monitored against source documentation and discrepancies will be sent as queries to the participating sites. Queries will be sent by MSKCC Research staff twice a month.

Participating sites should respond to data queries within 14 days of receipt.

16.1 Quality Assurance

Weekly registration reports will be generated to monitor patient accruals and completeness of registration data. Routine data quality reports will be generated to assess missing data and inconsistencies. Accrual rates and extent and accuracy of evaluations and follow-up will be monitored periodically throughout the study period and potential problems will be brought to the attention of the study team for discussion and action. Random-sample data quality and protocol compliance audits will be conducted by the study team, at a minimum of two times per year, more frequently if indicated.

16.1.1 Quality Assurance for Participating Sites

Each site participating in the accrual of participants to this protocol will be audited by the staff of the MSKCC study team for protocol and regulatory compliance, data verification and source documentation. Audits may be accomplished in one of two ways: (1) selected participant records can be audited on-site at participating sites or (2) source documents for selected participants will be sent to MSKCC for audit. Audits will usually be determined by participant accrual numbers and rate of accrual, but can also be prompted by reported SAEs or request of MSKCC PI.

Audits will be conducted at least once shortly after initiation of participant recruitment at a site, annually during the study (or more frequently if indicated), and at the end or closeout of the trial. The number of participants audited will be determined by available time and the complexity of the protocol.

The audit will include a review of source documentation to evaluate compliance for:

- Informed consent documents and procedures
- Adherence to eligibility criteria
- Protocol defined treatment
- Required baseline, on study and follow-up protocol testing
- IRB documents (submitted amendments, annual continuing review reports, SAEs)
- Required specimen submission
- Pharmacy review, if applicable
- Case Report Form submissions to MSKCC: timelines and accuracy

A wrap-up session will be conducted at the participating site and preliminary findings will be discussed with the participating site PI and research team. The preliminary results will be sent to the MSKCC PI.

Each audit will be summarized and a final report will be sent to the PI at the audited participating site within 30 days of the audit. The report will include a summary of findings, participant by participant case review, specific recommendations on any performance and/or shortcomings and request for corrective action, when necessary. When corrective action is required, the participating site must reply within 45 days of receipt of audit report with their corrective action plan.

IRB#: 07-022A(13)

A copy of the audit report and corrective action plan (if applicable) submitted by the participating site must be sent to the MSKCC IRB/PB, CRQA and maintained in the department's protocol regulatory binder.

16.1.2 Response Review

Since therapeutic efficacy is a stated primary objective, all sites participant's responses are subject to review by MSKCC's Therapeutic Response Review Committee (TRRC). Radiology, additional lab reports and possibly bone marrow biopsies and/or aspirates will need to be obtained from the participating sites for MSKCC TRRC review and confirmation of response assessment. These materials must be sent to MSKCC promptly upon request.

16.1.3 Data and Safety Monitoring

The Data and Safety Monitoring (DSM) Plans at Memorial Sloan-Kettering Cancer Center were approved by the National Cancer Institute in September 2001. The plans address the new policies set forth by the NCI in the document entitled "Policy of the National Cancer Institute for Data and Safety Monitoring of Clinical Trials" which can be found at: http://cancertrials.nci.nih.gov/researchers/dsm/index.html. The DSM Plans at MSKCC were established and are monitored by the Office of Clinical Research. The MSKCC Data and Safety Monitoring Plans can be found on the MSKCC Intranet at: http://mskweb2.mskcc.org/irb/index.html.

There are several different mechanisms by which clinical trials are monitored for data, safety and quality. There are institutional processes in place for quality assurance (*e.g.*, protocol monitoring, compliance and data verification audits, therapeutic response, and staff education on clinical research QA) and departmental procedures for quality control. Additionally, two institutional committees are responsible for monitoring the activities of our clinical trials programs. The committees, *Data and Safety Monitoring Committee (DSMC)* for Phase I and II clinical trials and the *Data and Safety Monitoring Board (DSMB)* for Phase III clinical trials, report to the Center's Research Council and Institutional Review Board. Patients treated collaborating institutions will also be included in these reviews.

During the protocol development and review process, each protocol will be assessed for its level of risk and degree of monitoring required. Every type of protocol (*e.g.*, NIH sponsored, in-house sponsored, industrial sponsored, NCI cooperative group, etc.) will be addressed, and the monitoring procedures will be established at the time of protocol activation.

16.2 Regulatory Documentation

Prior to implementing this protocol at MSKCC, the protocol, informed consent form, HIPAA authorization and any other information pertaining to participants must be approved by the MSKCC Institutional Review Board/Privacy Board (IRB/PB). Prior to implementing this protocol at the participating sites, approval for the MSKCC IRB/PB approved protocol must be obtained from the participating site's IRB.

The following documents must be provided to MSKCC before the participating site can be initiated and begin enrolling participants:

- Participating Site IRB approval(s) for the protocol, appendices, informed consent form and HIPAA authorization
- Participating Site IRB approved consent form
- Participating Site IRB membership list
- Participating Site IRB's Federal Wide Assurance number and OHRP Registration number
- Curriculum vitae and medical license for each investigator and consenting professional
- Documentation of Human Subject Research Certification training for investigators and key staff members at the Participating Site
- Participating site laboratory certifications and normals

Upon receipt of the required documents, MSKCC will formally contact the site and grant permission to proceed with enrollment.

16.2.1 Amendments

Each change to the protocol document must be organized and documented by MSKCC and first approved by the MSKCC IRB/PB. Upon receipt of MSKCC IRB/PB approval, MSKCC will immediately distribute all non-expedited amendments to the participating sites, for submission to their local IRBs.

Participating sites must obtain approval for all non-expedited amendments from their IRB within 90 calendar days of MSKCC IRB/PB approval. If the amendment is the result of a safety issue or makes the eligibility criteria more restrictive, sites will not be permitted to continuing enrolling new participants until the participating site IRB approval has been granted.

The following documents must be provided to MSKCC for each amendment within the stated timelines:

- Participating Site IRB approval
- Participating Site IRB approved informed consent form and HIPAA authorization

16.2.2 Additional IRB Correspondence

Continuing Review Approval

The Continuing Review Approval letter from the participating site's IRB and the most current approved version of the informed consent form should be submitted to MSKCC within 7 days of expiration. Failure to submit the re-approval in the stated timeline will result in suspension of study activities.

Deviations and Violations

A protocol deviation on this study is defined as a request to treat a research participant who does not meet all the eligibility criteria, pretreatment evaluation, or who requires alteration in their study plan. If a deviation from this protocol is proposed for a potential or existing participant at MSKCC or a participating site, approval from the MSKCC IRB/PB is required prior to the action. Participating sites should contact the MSKCC PI who will in turn seek approval from the MSKCC IRB/PB.

A protocol violation is anything that occurs with a participant, which deviated from the protocol without prior approval from the MSKCC IRB/PB. For protocol violations that are identified after they occur, the participating site should report to MSKCC as soon as possible. The MSKCC PI will in turn report the violation to the MSKCC IRB/PB.

Participating sites should report deviations and violations to their institution's IRBs as soon as possible per that site's institutional guidelines. Approvals/acknowledgments from the participating site IRB for protocol deviations and violations should be submitted to MSKCC as received.

Other correspondence

Participating sites should submit other correspondence to their institution's IRB according to local guidelines, and submit copies of that correspondence to MSKCC.

[figure not shown]
16.2.3 Document maintenance

The MSKCC PI and the Participating Site PI will maintain adequate and accurate records to enable the implementation of the protocol to be fully documented and the data to be subsequently verified.

The participating sites will ensure that all participating site IRB correspondence (IRB approval letters referencing protocol version date and amendment number, IRB approved protocol, appendices, informed consent forms, deviations, violations, and approval of continuing reviews) is maintained in the regulatory binder on site and sent to MSKCC.

A regulatory binder for each site will also be maintained at MSKCC; this binder may be paper or electronic.

After study closure, the participating site will maintain all source documents, study related documents and CRFs for 3 years.

16.3 Noncompliance

If a participating site is noncompliant with the protocol document, accrual privileges may be suspended and/or contract payments maybe withheld (if applicable), until the outstanding issues have been resolved.

17.1 PROTECTION OF HUMAN SUBJECTS

Prior to the enrollment of each patient, the risks, benefits and objectives of the study will be reviewed with the participant, including a discussion of the possible toxicities and side effects. Alternative options for treatment will be reviewed, including chemotherapy or hormonal therapy, as appropriate. Financial costs and burdens of the trial will be reviewed, including a detailed discussion of the tests that will be the financial responsibility of the study, and the tests which will be the financial responsibility of the patient.

17.2 Privacy

MSKCC's Privacy Office may allow the use and disclosure of protected health information pursuant to a completed and signed Research Authorization form. The use and disclosure of protected health information will be limited to the individuals described in the Research Authorization form. A Research Authorization form must be completed by the Principal Investigator and approved by the IRB and Privacy Board (IRB/PB).

17.3 Serious Adverse Event (SAE) Reporting

Any SAE must be reported to the IRB/PB as soon as possible but no later than 5 calendar days. The IRB/PB requires a Clinical Research Database (CRDB) SAE report be submitted electronically to the SAE Office at [contact]. The report should contain the following information:

Fields populated from CRDB:

- Subject's name (generate the report with only initials if it will be sent outside of MSKCC)
- Medical record number
- Disease/histology (if applicable)
- Protocol number and title

Data needing to be entered:

- The date the adverse event occurred
- The adverse event
- Relationship of the adverse event to the treatment (drug, device, or intervention)
- If the AE was expected
- The severity of the AE

IRB#: 07-022A(13)

- The intervention
 - Detailed text that includes the following
 - A explanation of how the AE was handled
 - A description of the subject's condition
 - Indication if the subject remains on the study
 - If an amendment will need to be made to the protocol and/or consent form.

The PI's signature and the date it was signed are required on the completed report.

17.2.1 Physician Reporting of Adverse Events

Patients in the treatment population will be followed for the development of AEs from study drug initiation through the end of study or 30 days after the end of treatment, whichever is longer. AEs and SAEs that develop during this period are followed until resolution or stabilization (resolved with sequelae). Only patients with clear documentation that no study drug was administered may be excluded from the treated population.

The safety/tolerability will be evaluated for treatment-emergent adverse events and serious adverse events, laboratory abnormalities, physical examinations, vital signs and patients experiencing dose modifications, dose interruptions, and/or premature discontinuation of study drug.

The investigator or designee must completely and promptly record each adverse event in the source documentation and in the appropriate CRF, regardless of relationship to study drug as determined by the investigator. The Principal Investigator must assess AE/SAE causality for any patients treated at his/her site and for any patients treated under the direct care of his/her sub-investigators. The investigator should attempt, if possible, to establish a diagnosis based on the patient's signs and symptoms. When a diagnosis for the reported signs or symptoms is known, the investigator should report the diagnosis, not the symptoms, as the adverse event.

Clinically significant laboratory abnormalities present at the Baseline visit will be recorded as pre-treatment signs and symptoms. Clinical Chemistry liver and renal function will be summarized using the NCI CTCAE for alkaline phosphatase, AST, ALT, total bilirubin, and creatinine. The number and percentage of patients that have each NCI CTCAE grade will be summarized using the most severe grade for the first cycle of therapy and for anytime during the study. The incidence of patients with clinically significant chemistry values (NCI CTCAE toxicity Grades of 3 or 4) that occurred after the first dose of study drug will be presented. Data for patients with clinically significant values will also be listed.

AEs and SAEs should be reported on the appropriate Case Report Forms. In addition, all SAEs must be reported promptly to AstraZeneca after the investigator recognizes/classifies the event as a SAE. The specific reporting time frame depends on the type of SAE. For life-threatening or fatal events, the investigator must report initial information on the SAE no later than the next business day, preferably by fax or alternatively by phone or email; at a minimum, a description of the event and the investigator's judgment of causality must be provided at the time of the

IRB#: 07-022A(13)

initial report. If a SAE is reported by phone or by e-mail, the investigator must fax a completed SAE report form to AstraZeneca within 24 hours. For an event that is not life-threatening or fatal, the investigator must fax a completed SAE report form within 2 business days after he/she recognizes/classifies the event as a SAE.

SAE reports should be faxed to AstraZeneca at: [name].

"Lack of efficacy" (progressive disease) is not considered an adverse event. The signs and symptoms or clinical sequelae resulting from lack of efficacy should be reported if they fulfill the adverse event of SAE definitions.

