6.1 CRITERIA FOR SUBJECT ELIGIBILITY

6.2 Subject Inclusion Criteria

A patient will be eligible for androgen receptor expression testing if the following criteria are met:

- Pathologically confirmed adenocarcinoma of the breast which is ER(-) and PR(-).
- Non-measurable or Measurable, metastatic disease

IRB#: 07-022A(13)

A patient will be eligible for participation in the therapeutic trial if the following criteria are met:

- Androgen receptor expression testing confirms that the patient's tumor is ER(-)/PR(-) /AR(+). ER, PR and AR are considered positive if greater than 10% of cell nuclei are immunoreactive. Receptor testing may be performed on either primary tumor specimen or tissue from a metastatic site.
- Prior neo-adjuvant or adjuvant chemotherapy is allowed. Any number of chemotherapy regimens are allowed for metastatic disease. There is no restriction on prior treatment with hormonal agents.
- Prior treatment with trastuzumab must have been given if patient has Her2/neu positive disease (defined as IHC=3+ or FISH amplified).
- At least 2 weeks since prior cytotoxic chemotherapy. Patients should have recovered from all acute effects of such therapy.
- Absence of active brain metastatic disease or leptomeningeal disease. If patient has a history of brain metastases, lesions must be stable for at least 3 months (as documented by either head CT or brain MRI).
- At least 4 weeks from major surgery with full recovery
- ECOG performance status 0-1
- Age 18 years or greater
- Laboratory parameters as follows:
 - \circ ANC $\geq 1.5 \times 10^9$ cells/L
 - \circ Platelets $\geq 100 \text{ x } 10^9 \text{ cells/L}$
 - $\circ \quad Hgb \geq 9g/dL$
 - AST (SGOT), ALT (SGPT) ≤ 2.5 x upper limit of normal range (ULN); total bilirubin ≤ 1.5 x ULN; alkaline phosphatase ≤ 2.5 x ULN (unless bone metastases are present in the absence of liver metastases), creatinine ≤ 1.5 mg/dL
- If female of childbearing potential, pregnancy test is negative
- If fertile, the patient agrees to use an effective method to avoid pregnancy for the duration of the study
- Informed consent has been obtained

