11.2.1 Adverse event

An adverse event is the development of an undesirable medical condition or the deterioration of a pre-existing medical condition following or during exposure to a pharmaceutical product, whether or not considered causally related to the product. An undesirable medical condition can be symptoms (*eg*, nausea, chest pain), signs (*eg*, tachycardia, enlarged liver) or the abnormal results of an investigation (*eg*, laboratory findings, electrocardiogram). In clinical studies, an AE can include an undesirable medical condition occurring at any time, including run-in or washout periods, even if no study treatment has been administered. In cancer clinical trials, many AEs are in fact related to progression of the patient's underlying malignancy.

An adverse event includes:

- An exacerbation of a pre-existing illness;
- An increase in frequency or intensity of a pre-existing episodic event or condition;
- A condition detected or diagnosed after study drug administration even though it may have been present prior to the start of the study;
- Continuously persistent disease or symptoms that were present at baseline and worsen following the start of the study.

IRB#: 07-022A(13)

An adverse event does not include:

- Medical or surgical procedures (eg, surgery, endoscopy, tooth extraction, or transfusion); however, the condition that leads to the procedure is an adverse event (Procedures that occur during the trial should be recorded on the Concurrent Procedure CRF);
- Pre-existing diseases, conditions or laboratory abnormalities present or detected at the start of the study that do not worsen;
- Hospitalizations or procedures that are done for elective purposes not related to an untoward medical occurrence (eg, hospitalizations for cosmetic or elective surgery or social/convenience admissions);
- The disease being studied or signs/symptoms associated with the disease unless more severe than expected for the patient's condition;
- Overdose of study drug without any clinical signs or symptoms.

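### The laboratory grade tables ignore baseline grade, so an unchanged high alkaline phosphatase at entry would be counted as a post-dose grade 3-4 abnormality

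*Combined protocol and SAP*

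**What the plan says.** Section 17.2.1 (Physician Reporting of Adverse Events) names the tests: "Clinical Chemistry liver and renal function will be summarized using the NCI CTCAE for alkaline phosphatase, AST, ALT, total bilirubin, and creatinine". For each grade, patient counts and percentages "will be summarized using the most severe grade for the first cycle of therapy and for anytime during the study". A second output gives the incidence of clinically significant chemistry values, described as "NCI CTCAE toxicity Grades of 3 or 4) that occurred after the first dose of study drug will be presented".

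The same paragraph mentions baseline once, as a matter of recording: "Clinically significant laboratory abnormalities present at the Baseline visit will be recorded as pre-treatment signs and symptoms". It closes with a patient listing: "Data for patients with clinically significant values will also be listed".

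Section 6.2 (Subject Inclusion Criteria) gives the entry limits for two of the tests as "alkaline phosphatase ≤ 2.5 x ULN (unless bone metastases are present in the absence of liver metastases), creatinine ≤ 1.5 mg/dL". AST and ALT may be at most 2.5 x ULN and total bilirubin at most 1.5 x ULN, with no exemption.

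For adverse events the rule is different. Section 11.2.1 excludes "Pre-existing diseases, conditions or laboratory abnormalities present or detected at the start of the study that do not worsen", and section 17.2.5 analyses treatment-emergent events, meaning those that start or get worse once study drug has begun.

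**The concern.** The trial has no control arm, so a patient's own baseline is the only comparator available within it. A table of worst post-dose grade that omits baseline cannot show whether a high value arose on drug or was already there.

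The problem is foreseeable here. Non-measurable disease is eligible, section 12.4 gives bone-only disease as its example, and the alkaline phosphatase limit is lifted "unless bone metastases are present in the absence of liver metastases". Section 11.3.4 repeats that exemption in its on-treatment rules, so the protocol itself treats this elevation as a special case. The laboratory tables do not.

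What is at stake is the reading of a descriptive safety table. Safety is a secondary objective, and section 3.3 reports no study in women above 25 mg per day, so readers will look at the liver tests with some care. With 28 patients, one or two carried-over values would visibly change the grade 3-4 line.

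**Working it through.** The plan states no figure on this point, so there is none to reproduce. The check has two parts.

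**1. The rules side by side, for one patient.** Take a patient with bone and no liver metastases whose alkaline phosphatase is grade 3 at baseline and grade 3 at every visit.

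- Entry (6.2): admissible, because the 2.5 x ULN limit is waived and no other limit replaces it.
- Adverse event definition (11.2.1): not an adverse event, because the value has not worsened.
- Treatment-emergent analysis (17.2.5): not counted, because nothing began or worsened.
- Each-grade table (17.2.1): counted at grade 3, both for cycle 1 and for any time on study.
- Grade 3-4 incidence (17.2.1): counted, because a grade 3 value was seen after the first dose.

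The other four tests differ. AST, ALT, bilirubin and creatinine are capped at entry for everyone, and alkaline phosphatase is capped for every patient outside the exempt group. If those caps lie below grade 3, unchanged baseline values can reach only the lower rows of the each-grade table. The documents do not reproduce the CTCAE version 3 cut-offs, so this is an assumption.

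**2. Size.** Inputs: n = 28 (section 14.0), taking all 28 as treated and tabulated. Let b be the share of patients in the exempt group and q the share of those whose baseline alkaline phosphatase is grade 3-4 and stays so. The documents give neither b nor q; the values below are assumptions.

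Per patient: 1/28 = 3.6 percentage points; 2/28 = 7.1; 3/28 = 10.7.

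Expected number = 28 x b x q; percentage points = 100 x b x q; chance of at least one = 1 - (1 - bq)^28.

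| b | q | Expected patients | Points | Chance of at least one |
|---|---|---|---|---|
| 0.20 | 0.02 | 28 x 0.004 = 0.11 | 0.4 | 1 - 0.996^28 = 11% |
| 0.30 | 0.10 | 28 x 0.03 = 0.84 | 3.0 | 1 - 0.97^28 = 57% |
| 0.50 | 0.20 | 28 x 0.10 = 2.8 | 10.0 | 1 - 0.90^28 = 95% |

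The range runs from almost nothing to about three patients. Only the 3.6 points per patient follows from the documents alone.

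**The case against.** The strongest reply is that baseline is not ignored. Clinically significant baseline abnormalities are recorded as pre-treatment findings, patients with grade 3-4 values are listed, and with 28 patients a careful reader could match the two. Section 14.0 also promises summaries of changes in continuous variables. This softens the consequence but leaves the count as it is: the recording sentence governs data capture, the listing is not said to show baseline values, and the summaries of change are generic and not tied to grade.

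The grade 3-4 sentence could also be read as meaning new onset. If that is the intent, the text does not say so, and the each-grade table would still have no baseline condition.

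The reply does stand against several stronger readings that a reader might draw:

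- *That pre-existing disease is counted as toxicity in the adverse event analysis.* Sections 11.2.1 and 17.2.5 exclude it. They govern a different output from the laboratory tables, so the two rules differ without formally contradicting each other.
- *That any patient may enter with unlimited alkaline phosphatase.* The waiver covers only those with bone and no liver metastases.
- *That liver and renal results are distorted generally.* The other four tests are capped at entry. The hepatitis warning in Appendix A turns on transaminases, ALT in particular, and these are among the capped tests.
- *That the 5% rate of increased alkaline phosphatase in Appendix A is a yardstick.* It concerns men on 50 mg with an LHRH analogue, regardless of causality and not restricted to grade 3-4.

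**Conclusion.** The concern holds in a narrow form. Followed as written, section 17.2.1 would count an unchanged high baseline alkaline phosphatase as a post-dose grade 3-4 abnormality in patients admitted under the bone-metastasis exemption. Each such patient adds 3.6 percentage points. How many there would be cannot be derived from the documents; under the assumptions shown, the expected number is 0.1 to 2.8 of 28. For the four capped tests the effect is at most on the lower rows of the each-grade table, provided the caps lie below grade 3.

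A reader might infer that comparing with baseline would isolate the drug's effect. It would not: a rise caused by progressing bone or liver metastases would still show as worsening, and a single-arm trial cannot resolve that.

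No decision rule uses these tables. The primary endpoint, the 4-of-28 rule and the tolerability percentage in section 14.0 are unaffected. Severity: minor.

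**What to change.** In section 17.2.1:

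- For the five tests, present a shift table from baseline grade to worst post-dose grade, for the first cycle and for any time on study.
- Count as a post-dose grade 3-4 abnormality only a grade 3-4 value of a higher grade than that patient's baseline.
- List unchanged baseline abnormalities separately, with the baseline and worst post-dose values, so that a rise within one grade remains visible.

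The cost is a sentence or two of text and one table. Baseline chemistry (section 8.1) and chemistry every 4 weeks (section 10.0) are already collected, so no new data, visits or patients are needed.
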